## 1.0 PROTOCOL SUMMARY AND/OR SCHEMA

This is an NCI funded (**U01CA157442-01A1**) study to assess the prognostic value of fluorine-18-labeled fluoro-misonidazole (F-FMISO), a hypoxia radiotracer, in patients with non-small cell lung cancer (NSCLC) who are treated with definitive conventionally fractionated radiation therapy (RT), neoadjuvant chemotherapy, or chemo-RT. The secondary goal will be to assess the predictive value of F-FDG, a metabolic rate radiotracer, in a second group. Please note that all patients entered on this protocol will undergo the standard of care treatment for NSCLC. The information obtained from the use of investigational F-FDG and F-FMISO PET scans will NOT be used to manage patients' treatment on this protocol.

### Schema:

There are two groups currently active in this protocol. Group 1 includes a mid-treatment FMISO PET scan and FDG PET scan. Group 2 includes a sequential injection of F-FMISO and F-FDG. Both groups will have completed a routine pre-treatment FB and breath-hold F-FDG PET/CT and pre-treatment F-FMISO PET Scan.

- Group 1: Perform a routine pre-treatment free-breathing (FB) and breath-hold (for only one PET Field of View, i.e. an additional ~10 min of PET/CT imaging) F-FDG PET/CT. If the patient is planned to receive radiotherapy, the FB PET/CT scan will be used for RT planning.
- Group 2: Perform a routine pre-treatment free-breathing (FB) F-FDG PET/CT. If the patient is planned to receive radiotherapy, the FB PET/CT scan will be used to RT planning.
- Both groups will perform a pre-treatment dynamic F-FMISO PET scan (F-FMISO1). This scan will occur at least one day after the baseline F-FDG PET/CT scan, but prior to initiation of therapy. A baseline F-FDG PET/CT scan may be acceptable provided it is not earlier than one month prior to the F-FMISO study and will assist to define the field of view of the dynamic F-FMISO PET scan. If a CT is available to allow definition of the tumor region, then the F-FMISO may be performed before the FDG PET scan. Dynamic F-FMISO PET images will be corrected for breathing-induced artifacts allowing kinetic analysis to be performed for both the motion-corrected and the free-breathing dynamic PET image sets. The degree of hypoxia within the tumor volume will be estimated by the magnitude of the F-FMISO irreversible trapping rate constant.
- **Group 1 : F-FMISO2/FDG mid-treatment PET/CT:** Perform a mid-treatment dynamic F-FMISO (FMISO2) PET/CT (following the same protocol as for the baseline FMISO) scan in a group of twenty five patients, undergoing RT or concurrent chemo-RT. This scan will occur two weeks +/- 4 days after the start of radiotherapy or the radiation portion of combined chemo-radiation (Diagram 1).
- Perform a mid-treatment F-FDG PET/CT scan in a group of twenty five patients, undergoing RT or concurrent chemo-RT. This scan will occur two to three weeks +/- 4 days after start of treatment of radiotherapy or the radiation portion of combined chemo-radiation. F-FDG PET/CT scans will be performed in both Free-Breathing (FB) and Breath-Hold (BH) modes. The predictive value of F-FDG, based on the change in lesion SUVpeak between baseline and the 3-week mid-treatment

scan and following the PERCIST criteria, will be assessed using both the FB, and the BH, image sets independently. Results deduced from the FB and BH data sets will be compared and correlated with outcome.

- **Group 2: Combined  $^{18}\text{F}$ -FMISO/ $^{18}\text{F}$ -FDG baseline PET/CT:** In a group of 5 patients, two PET radiotracers  $^{18}\text{F}$ -FMISO and  $^{18}\text{F}$ -FDG will be injected sequentially into the patient. Since all PET radiotracers emit the same 511 keV coincidence photons, it is not possible to discriminate events from these different radiotracers. However, by conducting a dynamic PET/CT scan with staggered  $^{18}\text{F}$ -FMISO and  $^{18}\text{F}$ -FDG injections (45min +/- 15min apart), the kinetic profiles should provide sufficient information to allow signals from the two radiotracers to be clearly separated. This sequential  $^{18}\text{F}$ -FMISO /  $^{18}\text{F}$ -FDG study will be performed at least one day after the sole FMISO1 radiotracer baseline PET/CT scan, and prior to the initiation of therapy. The  $^{18}\text{F}$ -FMISO and  $^{18}\text{F}$ -FDG individual signals will be deduced from the combined dynamic PET images by means of kinetic modeling, and the corresponding radiotracers entrapments within the tumor will be determined. The accuracy of the  $^{18}\text{F}$ -FMISO signal extraction from the combined one in the staggered  $^{18}\text{F}$ -FMISO/ $^{18}\text{F}$ -FDG dynamic PET/CT study will be assessed by comparison to that deduced from the sole FMISO1 study (Diagram 2).

[figure not shown]

Diagram 1. Combined  $^{18}\text{F}$ -FMISO/ $^{18}\text{F}$ -FDG baseline PET/CT

[figure not shown]

Diagram 2. Group 2: Sequential FDG and FMISO treatment group

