### **3.4 Simultaneous imaging of tumor hypoxia and tumor metabolism**

Imaging hypoxia and metabolism simultaneously may provide a new understanding of the role of the tumor microenvironment; in particular the interplay between hypoxia (defined by FMISO) and tumor cell metabolism (defined by FDG).

F-FMISO and FDG have been shown to be important prognostic and predictive biomarkers in patients undergoing CRT [59, 60]. Identifying simultaneously hypoxic and metabolically active sub-regions within the tumor is a more coherent measurement of the tumor microenvironments than co-registering images acquired in different imaging sessions where temporal changes in the biology and inaccuracies in the image registration curtail the integrity of the data. Previous studies have demonstrated both the feasibility and potential for simultaneous assessment of two physiological processes (mainly in brain) by exploiting temporal [61] kinetic, or daughter outputs (positron vs positron+cascade  $\gamma$ ) (44) differences between radiotracers.

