## **9.2 F-FMISO PET/CT Scan Protocol:**

The first F-FMISO PET/CT scan will be performed within 14 days (+/- 5 days) after the baseline F-FDG scan, and before starting therapy. Dynamic FMISO PET scans will be performed on one of the GE Discovery PET/CT scanners residing in the nuclear medicine department at MSKCC. The patient will be set up in treatment position with intra-venous lines for radiotracer injection and for venous blood sampling. One 370 MBq (10 mCi) +/- 10% dose of F-FMISO will be injected as a bolus, and the dynamic scan initiated coincident with the injection.

Dynamic F-FMISO PET data will be acquired in List Mode and reconstructed in time frames that display the kinetics of tumor uptake. The total duration of the study is approximately 3 hours. The patient is injected in the PET scanning position on the couch and PET data acquired from 0-40 min. The patient is then allowed to return to the waiting room and rest. There are two further scan segments at approximately 90 min and 180 min post injection each of 10-minute duration. The total PET scan time within the 3 hour imaging session is therefore only 60 minutes. No further radioactivity will be injected for the 2nd and 3rd PET scan segments. In all three sessions of the dynamic PET study, the patient's breathing signal will be recorded simultaneously using the in-house developed tracking described previously. The respiratory signal will be used to retrospectively identify those PET events that occurred at end-expiration. Those events will be selected retrospectively to generate a dynamic PET data set corresponding to end-expiration (BH-dyn PET), motion-free PET images.

In each of the three dynamic sessions, a 4D-CT (10mA) scan and a BH-CT (10mA) scan (at end-expiration) of a 15cm segment of the body (the field of view of the PET scanner) will be performed with the tumor at the field center. These images will be used for both attenuation correction and registration of the serial image set, for the free-breathing and BH PET dynamic data sets respectively.

To further facilitate patient image registration, external fiducial markers may be placed on the patient's thorax.

A second set of three dynamic F-FMISO scans will be performed following the same sequence as outlined above for the baseline dynamic F-FMISO study, at 2 to 3 weeks (+/- 4 days) post-initiation of therapy.

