#### **9.4 Simultaneous $^{18}\text{F}$ -FDG/ $^{18}\text{F}$ -FMISO PET/CT Scan Protocol:**

[figure not shown]
Simultaneous Dynamic PET  $^{18}\text{F}$ MISO/ $^{18}\text{F}$ DG scan will be performed at least one day after the sole baseline  $^{18}\text{F}$ MISO PET/CT, but preceding chemo- or radiation therapies. Dynamic PET/CT data will be acquired over the same single FOV as for the sole baseline  $^{18}\text{F}$ MISO PET/CT described above. CT images will be acquired for PET attenuation correction purpose. Imaging will start simultaneously with the intravenous bolus injection of  $^{18}\text{F}$ -FMISO (8 mCi +/- 10%). PET data will be acquired in list mode (LM). The dynamic acquisition will last for up to a total of 120 min. 8 mCi (+/- 10%) of  $^{18}\text{F}$ DG will be injected intravenously 45 min +/- 15 min after the  $^{18}\text{F}$ -FMISO injection, and without interruption of the dynamic PET acquisition. One additional 10 min dynamic PET scan will be performed at 180 min post-FMISO injection. If the patient cannot tolerate the length of the first imaging session, an additional 10 min dynamic PET scan may be performed at 90 min +/- 10 min. Blood samples may be withdrawn following the same protocol as for the sole FMISO dynamic study described above.

For each of the imaging sessions a 4DCT at 10mA and a CT-BH (40mA and 1-mA for the first session and the subsequent sessions respectively) will be performed for attenuation correction,

All PET and CT data will be acquired and recorded in a secure patient database. During all imaging sessions, patients will be immobilized in RT alpha cradle if available and tolerable.

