## 10.0 EVALUATION DURING TREATMENT/INTERVENTION

There will be no specific monitoring after the studies. All patients will be evaluated according to the standard of care for their lung cancer. Their imaging studies performed as part of standard of care every 3-4 months and their vital status will be periodically monitored for 3 years following treatment for the progression free survival and overall survival analyses.

	Day 0  BH F-FDG  PET/CT	F-FMISO1  (within 14 +/- 5 days after the baseline  F-FDG scan, and before starting therapy)	Mid Treatment Scans		Follow up
			F-FMISO2  Within occur two weeks +/- 4 days post initiation of therapy	F-FDG  (FDG: 3 to 4 weeks +/- 4 days post-initiation of therapy)	
Informed consent	X				
Review of your history and medication	X				
Physical exam	X				
Vital signs	X	X			
Standard clinical  F-FDG PET/CT scan	X		X		
 F-FMISO tracer injection		X 	X 	X	
Research PET scans	X	X	X	X	
Research blood draws		X	X		
Review of medical record for PFS and OS					X
Standard clinical CT of the chest					X 
Vital signs and Toxicity assessment 		X	X		

Table 1. Group 1: FMISO 2 Mid-Treatment Group Study Outline

	Day 0  F-FDG PET/CT	F-FMISO1  (within 14 +/- 5 days after the baseline  F-FDG scan, and before starting therapy)	Simultaneous F-FDG/F-FMISO 2  (at least one day after the first  F-FMISO scan but before starting therapy. This must also be within 14 +/- 5 days after baseline FDG scan)	Optional Mid Treatment F-FDG  (3 weeks +/- 4 days after RT)	Follow up
Informed consent	X				
Review of your history and medication	X				
Physical exam	X				
Vital signs	X	X			
Standard clinical  F-FDG PET/CT scan	X		X		
 F-FMISO tracer injection		X 	X 	X	
Research PET scans	X	X	X	X	
Research blood draws		X	X	X	
Review of medical record for PFS and OS					X
Standard clinical CT of the chest					X 
Vital signs and Toxicity assessment 		X			

Table 2. Group 2: Simultaneous FDG and FMISO group study outline

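### The Group 2 accuracy test compares FMISO signals from different days and frame schedules, so the difference cannot be read as separation error alone

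*Combined protocol and SAP*

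**What the plan says.** The Schema (section 1.0) sets the size of this part with the words "In a group of 5 patients, two PET radiotracers" and says that accuracy of the extracted FMISO signal in the two-tracer "dynamic PET/CT study will be assessed by comparison to that deduced from the sole FMISO1 study". On timing, the sequential "study will be performed at least one day after the sole FMISO1 radiotracer baseline PET/CT scan, and prior to the initiation of therapy". Table 2 in section 10.0 adds, for the dual scan, "This must also be within 14 +/- 5 days after baseline FDG scan".

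The two acquisitions differ:

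- **Sole FMISO (section 9.2).** "One 370 MBq (10 mCi) +/- 10% dose of" FMISO is given. "The patient is injected in the PET scanning position on the couch and PET data acquired from 0-40 min" Two 10-minute segments follow, at about 90 and 180 minutes.
- **Dual scan (section 9.4).** FMISO is given at 8 mCi +/- 10%, with FDG 45 +/- 15 minutes later. "The dynamic acquisition will last for up to a total of 120 min" One further 10-minute scan follows at 180 minutes.

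Section 3.4 favours one session over co-registering images from several, "where temporal changes in the biology and inaccuracies in the image registration curtail the integrity of the data". It also counts freedom from transient biological change between scans as a benefit of the dual method. Section 14.0 contains no analysis, agreement limit or acceptance criterion for the dual-tracer comparison.

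**The concern.** The feasibility question is whether the FMISO signal can be recovered correctly once FDG has been added. The comparison with FMISO1 answers a broader one: how closely does FMISO recovered on one day agree with FMISO measured alone on another? A sound method could look inaccurate because k3 moved between days or because the frames sample the curve differently. Apparent agreement in five patients is also weak evidence that the method is accurate. Section 3.4 makes clinical feasibility the condition for a later study in a larger cohort, so what this comparison can and cannot show should be settled before it is reported.

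**Working it through.** The plan gives no precision figure for this comparison, so there is none to reproduce.

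**Inputs.** From the documents: n = 5 dual-scan patients, with one dual-minus-sole difference each. Assumed, because the documents give no value: the per-scan day-to-day CV of k3, written w, at 5%, 10% and 20%. The random separation error CV is s. Errors are taken as independent and roughly normal on the relative scale.

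**Step 1: what the difference contains.** Var(difference) = 2w² + s². One difference per patient estimates only the sum. An observed SD of 30% fits each of these equally well:

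- w = 0%, s = 30%
- w = 10%, s = sqrt(0.30² - 2 × 0.10²) = 26.5%
- w = 20%, s = sqrt(0.30² - 2 × 0.20²) = 10%
- w = 21.2%, s = 0%

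**Step 2: spread with perfect separation (s = 0).** The SD is sqrt(2) × w and the limits of agreement are +/-1.96 × SD. With n = 5, the 95% half-width for mean bias is t(0.975, 4 df)/sqrt(5) × SD = 2.776/2.236 × SD = 1.24 × SD.

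| w (assumed) | SD of difference | Limits of agreement | Half-width for mean bias |
|---|---|---|---|
| 5% | 7.1% | +/-14% | +/-9% (8.8%) |
| 10% | 14.1% | +/-28% | +/-18% |
| 20% | 28.3% | +/-55% | +/-35% |

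**Step 3: how visible a real separation error is.** Adding s = 10% raises the SD from 7.1% to 12.2% at w = 5%, from 14.1% to 17.3% at w = 10%, and from 28.3% to 30.0% at w = 20%. With five patients, the 95% interval for the SD itself runs from 0.60 to 2.87 times its estimate.

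**Step 4: would a test-retest benchmark settle it?** Suppose repeat sole-FMISO baseline pairs existed under the same acquisition. A one-sided 5% F test of the dual-minus-sole variance against the test-retest variance, with five dual patients, would have this power:

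- s = w (variance ratio 1.5): about 10% with 5 pairs, 15% with 25.
- s = 2w (variance ratio 3.0): about 24% with 5 pairs, 47% with 25.

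**Step 5: the interval between scans.** If Table 2 means by day 14 + 5 = 19 and FMISO1 is on day 1, the gap can reach 19 - 1 = 18 days. If it means a window from day 9 to day 19, the gap is at most 10 days. Section 11.2.1 says that two FMISO scans fall within 5 days. The Schema and section 4.2 also allow FMISO1 to precede FDG. No upper bound is firm.

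**The case against.** Several objections carry weight.

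- **Earlier validation.** Section 3.4 reports validation in simulations and animal models, so the FMISO1 comparison is an added in-vivo step and not the only evidence. Both tracers emit the same photons, so no second FMISO-only tumour image covering the period after FDG injection is available in the dual session. Some between-day reference is unavoidable. This stands, and is why the comparison should be kept.
- **Section 3.4 concerns spatial overlap.** A reader might infer that the protocol itself calls this comparison unsound. It does not. The sentence is about co-registering hypoxic and metabolic sub-regions across sessions. It does acknowledge that biology changes between sessions, and only that is used here.
- **Activity.** Under linear tracer kinetics, 10 against 8 mCi mainly affects noise, not k3. This stands. Frame timing is the more relevant difference, and list-mode data allow frames to be matched.
- **FMISO-only start.** The first 30 to 60 minutes of the dual scan contain FMISO alone, a partial internal reference. But separation error arises after FDG injection, in the later data that inform trapping, and no such internal check is planned.
- **A benchmark is written in.** Sections 9.3, 11.2.1 and 14.0 describe two baseline FMISO scans, and section 14.0 a reproducibility analysis by kappa and concordance correlation. But the Schema and Tables 1 and 2 schedule no repeat sole baseline scan: Group 1's second FMISO scan is mid-treatment and Group 2's is the dual scan. Nothing links reproducibility to this test, and Step 4 shows limited power even if it were linked.
- **Small feasibility aim.** It is secondary, involves five patients and does not guide care. This limits the consequence but does not separate the sources of error.

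**Conclusion.** The point holds as one of interpretation. The FMISO1 comparison measures separation error plus day-to-day change plus acquisition differences, and should not be reported as separation accuracy alone. Its size depends on a CV that the documents do not give: limits of agreement of about +/-14%, +/-28% or +/-55%, and mean bias known to about +/-9%, +/-18% or +/-35%, at CVs of 5%, 10% and 20% with perfect separation.

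Three stronger readings are tempting but unsupported. First, that a systematic error of 10-15% is bound to be hidden: it falls inside the half-width for mean bias at a CV of 10% or 20%, but outside it at 5%. Second, that the scans may be 18 days apart: this is one reading of Table 2, and section 11.2.1 points elsewhere. Third, that the study would wrongly adopt or drop dual-tracer imaging: there is no adoption rule, and section 3.4 leaves comparative value to a larger future study.

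**What to change.** 1. **Keep the FMISO1 comparison and relabel it.** Describe it as agreement reflecting separation error plus between-day variation. After separation, fit the kinetics in both sessions on the shared frames (0-40, about 90-100 and 180-190 minutes), and report this beside the full-data fit.
2. **Add a supplementary same-data check.** Combine each patient's fitted FMISO1 tumour and blood curves with a range of plausible FDG curves, including that patient's own estimate, at the actual injection delay and with dual-session noise. Run the separation and report bias and SD of the recovered k3 and hypoxic fraction.
3. **State the limits of that check.** FMISO1 has no data at about 40-90 and 100-180 minutes, so its curve must be interpolated from the model there. The patient's own FDG estimate comes from the method under test, hence the range of FDG curves. The check covers identifiability and noise, not model misspecification or chromatography error, and does not replace the in-vivo comparison.
4. **Reconcile the text.** Table 2 and section 11.2.1 must agree on scan timing. The twice-at-baseline text in sections 9.3, 11.2.1 and 14.0 must agree with the Schema and tables.

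The cost is modest extra analysis on five patients, with no new scan or injection.

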## 2.0 OBJECTIVES AND SCIENTIFIC AIMS

The primary objectives of this study are:

- To correlate the presence and extent of hypoxia, as defined by F-FMISO FB and BH PET/CT at baseline with 3-year progression-free survival (PFS) and overall survival (OS).
- To assess the predictive value of F-FMISO PET/CT in lung cancer patients undergoing radiotherapy or concurrent chemoradiotherapy, as measured by Breath-Hold (BH) and Free-Breathing (FB) PET/CT images, and to determine whether BH PET/CT provides greater predictive capability than Free-Breathing (FB) PET/CT.

The secondary objective of this study is:

- To assess the predictive value of F-FDG PET/CT in a group of twenty five lung cancer patients undergoing radiotherapy or concurrent chemoradiotherapy, as measured by Breath-Hold (BH) and Free-Breathing (FB) PET/CT images, and to determine whether BH PET/CT provides greater predictive capability than Free-Breathing (FB) PET/CT.

- To assess the feasibility of simultaneous F-FDG and F-FMISO PET dynamic acquisitions in a group of 5 patients undergoing radiotherapy or concurrent chemoradiotherapy. If successful, our approach would allow multi-radiotracer PET exams on the same day reducing the need for extra patient visits. For the patients who will undergo the dual FMISO/FDG study, the mid-treatment FMISO will be optional.

### **3.0 BACKGROUND AND RATIONALE**

#### **3.1 F-FDG PET/CT**

F-FDG PET is a non-invasive molecular imaging tool that has been shown to have a major impact on the diagnosis and staging of NSCLC, as well as in treatment planning of radiotherapy and detection of recurrent disease (1-4). Its prognostic and predictive values in NSCLC have been well demonstrated (5)

In a pilot study that included 15 patients, a reduction in F-FDG uptake of more than 50% between pre- and post- induction chemotherapy in the primary tumor or mediastinal clearance was shown to be a better predictor of long-term survival (6) compared with the standard WHO criteria used for response assessment on CT. In another multi-center study that evaluated F-FDG-PET before and after 1 and 3 cycles of induction chemotherapy the residual metabolic rate of glucose after completion of induction chemotherapy appeared to be the most prognostic factor (7). Its predictive value with respect to therapy outcome of combined chemo-radio therapy has also been demonstrated (8-10). Currently, no early markers of tumor response to radiation therapy are in existence or in clinical use. While FDG-PET has become a standard modality for staging and re-staging of NSCLC, its value as an early response marker during radiation therapy remains unclear. The University of Michigan tested the value of a mid-treatment FDG-PET scan at 45 Gy in 15 patients (11). The qualitative response during RT correlated with the overall response post-RT. However, the later during the treatment course the PET scan is performed, the lesser are the chances of making adjustments to the initial first-line treatment, as the majority of the RT dose is already delivered at 45 Gy. Therefore, we are planning to perform the FDG-PET scan at an earlier time point of 3 weeks at a dose of approximately 30 Gy. This will provide the basis for early tumor assessment and adaptive radiation therapy strategies that would take into account an early tumor response. It would allow stratification of patients into favorable and unfavorable responders and the development of individually tailored strategies for these patients.

Consequently, F-FDG-PET can form the basis for clinical trials evaluating the feasibility of adopting therapy based on response assessment (12-15).

Due to patient breathing, FDG PET quantitation may become susceptible to breathing-induced uncertainties, which may reduce the prognostic and predictive values of FDG-PET. Breath-Hold PET/CT acquisition has been shown to improve the accuracy of PET quantitation. In contrast to the study by Kong et al. (11), we will therefore measure the prognostic and predictive values of FDG PET using BH PET data, and compare those with results deduced from the free-breathing data sets. Due to the improved accuracy of BH-PET quantitation, we expect BH data would yield improved prognostic values over those of the FB PET.

